Hypothesis: Loteprednol 0.5% gel will perform similarly or better than a regimen of prednisolone acetate 1% and fluorometholone 0.1% in the prevention of visually significant postoperative corneal haze after photorefractive keratectomy (PRK) with a lower incidence of intraocular pressure elevation.

Objectives: We aim to conduct a prospective, randomized trial to compare the incidence of intraocular pressure rise and visually significant postoperative corneal haze after PRK with the use of loteprednol 0.5% gel compared to the use of earlier generation steroids, prednisolone acetate 1% suspension and fluorometholone 0.1% suspension.

Patients undergoing PRK will be assigned to 1 of 2 postoperative steroid regimens. Group 1 will use only loteprednol 0.5% gel, tapered off slowly based on clinical evaluations of the corneal healing response. Group 2 will use prednisolone acetate 1% suspension tapered down to a regimen of fluorometholone 0.1% which will then be tapered off based on clinical evaluations of the corneal healing response. If no difference in efficacy or safety is detected between these two regimens, this study will support the use of either steroid regimen in patients after PRK. If there is a major difference in the efficacy or safety of these two regimens, this could influence post-refractive surgery treatment practices.

7. Is this a multi-site study, where more than one site needs IRB approval?

Yes No

8. Background and Introduction:

In photo-ablation procedures, an excimer laser is used to sculpt corneal tissue to correct refractive error. During PRK, the surface epithelium is removed and the laser energy is applied to reshape the underlying corneal stroma. This procedure is FDA approved and used widely. Corneal haze is a well known and a potentially vision threatening postoperative complication of PRK. Topical ophthalmic corticosteroids are routinely prescribed by most surgeons postoperatively to help prevent this complication.

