Prior to surgery, patients will be randomly assigned to one of two postoperative steroid regimens. Group 1 will use loteprednol 0.5% gel in both eyes, starting at a frequency of four times per day for the first week and then tapered off based on clinical judgement of the corneal healing response. Group 2 will use prednisolone acetate 1% suspension in both eyes, starting at a frequency of four times per day for the first week, then tapered down to a regimen of fluorometholone 0.1% suspension, which will then be tapered off based on clinical judgement of the corneal healing response.

All surgical procedures will be performed according to the standard of care and the surgeons' standard practices. The study outcome measures are standard of care for pre-operative and post-operative evaluation of refractive surgery patients.

The primary outcome measure will be intraocular pressure at each study time point. Secondary outcomes will be grade of corneal haze, manifest refraction, best corrected visual acuity, and uncorrected visual acuity.

Study outcome measures will be evaluated for each treated eye of each subject at each study time point. Routine clinical management may be altered if the intraocular pressure is elevated sufficiently to require medical intervention, if there is significant postoperative corneal haze, or if there are other postoperative complications. In these situations, additional IOP lowering drops may be added or the steroid decreased, changed, or increased, based on the clinical picture and physician judgement. Additional examinations between study time points may be performed as necessary according to the surgeon's usual care, but will not be considered part of the study data. Patients have the right to withdraw at any time and future medical care will not be influenced by their lack of participation.

If enhancement surgery is deemed necessary and performed during the one-year post-operative period, study data collection will end for that eye at the time of the enhancement. All prior data collected will still be included in the statistical analysis and if only one eye requires enhancement, data collection will continue on the fellow eye until the last planned study time point.

Eyes will be evaluated with the following procedures:

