- Intraocular pressure (by applanation tonometry): Pre-operatively and post-operative week 1 (\pm 3 days), month 1 (\pm 10 days), month 2 (\pm 10 days), month 3 (\pm 14 days), month 6 (\pm 1 month), and month 12 (\pm 1 month)

Note: Intraocular pressure will be measured by a technician or physician who is masked to the treatment regimen of the patient at each visit.

- Grade of corneal haze (Fantes scale): Post-operative Month 1 (\pm 10 days), month 2 (\pm 10 days), month 3 (\pm 14 days), month 6 (\pm 1 month), and month 12 (\pm 1 month)

Note: Corneal haze will be graded by a study physician who did not perform the original surgery and is masked to the treatment regimen of the patient at each visit.

- Manifest refraction (sphere, cylinder, and axis): Pre-operatively and post-operatively month 1 (\pm 10 days), month 2 (\pm 10 days), month 3 (\pm 14 days), month 6 (\pm 1 month), and month 12 (\pm 1 month)

- Best corrected visual acuity: Pre-operatively and post-operatively month 1 (\pm 10 days), month 2 (\pm 10 days), month 3 (\pm 14 days), month 6 (\pm 1 month), and month 12 (\pm 1 month)

- Uncorrected visual acuity: Pre-operatively and post-operative day 1 (\pm 1 day), week 1 (\pm 3 days), month 1 (\pm 10 days), month 2 (\pm 10 days), month 3 (\pm 14 days), month 6 (\pm 1 month), and month 12 (\pm 1 month)

- Pupil size measured in the dark: Pre-operatively only

- Corneal pachymetry: Pre-operatively only

Data and Safety Monitoring:

There is no formal data and safety monitoring board for this study. All treatments, procedures, and testing being performed in the study are within the standard of care and treatment for PRK patients. This study does not put study participants at any known increased risk beyond that normally assumed by patients undergoing PRK outside the study. The investigators feel that the standard processes for identifying and reporting adverse events (AE) are sufficient to safeguard the well-being of study participants.

The investigators have a nomogram from which they work and therefore have expected vision outcomes for patients on an individual basis. It is routine practice to compare actual with expected outcomes as a quality assurance measure. Should any concerns arise prior to completion of the study, a safety analysis will be conducted immediately.

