Yes No

If no, list the procedures that are performed for research purposes only (non-standard or non-standard of care procedures):

Only data collection and analysis are for research purposes only. All other procedures are within the standard of care.

8. Is there a safety monitoring plan for this study?

Yes No

9. Provide a summary of the statistical methods, data analysis, or data interpretation planned for this study. Factors for determining the proposed sample size (e.g., power) should be stated.

Standard statistics will be calculated and used to describe the two treatment groups in terms of all study variables: intraocular pressure, grade of corneal haze, manifest refraction, best corrected visual acuity, and uncorrected visual acuity. Statistics will be compiled for each variable at the study time points listed in the data collection protocol. Patients withdrawn from the study prior to surgery will not be included in the data analysis and will be replaced in the enrollment group. For eyes that require enhancement surgery, only data collected prior to the enhancement surgery will be included in the statistical analysis.

Prior studies have considered intraocular pressure elevation of greater than or equal to 10 mm Hg above baseline clinically significant. A prior study of healthy volunteers demonstrated an incidence of IOP elevation > 10 mm Hg of 1.95% in patients using loteprednol eye drops versus 7.48% in patients using dexamethasone eye drops [1]. Using these expected proportions, an alpha of 0.05, and a power of 80%, we would need a sample size of 230 patients (460 eyes). In order to account for about 10% dropout, we intend to enroll 250 patients in the study, 125 in the loteprednol arm and 125 in the prednisolone and fluorometholone arm.

IRB_00075978

Created: 8/9/2014 9:53 AM

IRB_00075978

PI: [name]

Submitted: 8/20/2014

View: 4.2 Consent Process

Title: Efficacy and safety of loteprednol 0.5% gel for routine prophylaxis after photorefractive keratectomy compared to prednisolone acetate 1% suspension and fluorometholone 0.1% suspension

Consent Process

1. The following investigators and internal staff will obtain consent (as indicated on the Study Location and Sponsors Page):

[name] University of Utah

[name]

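### The aim and sample size concern the incidence of IOP rise, but extra examinations are excluded, so a rise found and treated only between scheduled visits counts as no rise in the IOP analysis

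*Combined protocol and SAP*

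**What the plan says.** The Objectives set out to "compare the incidence of intraocular pressure rise and visually significant postoperative corneal haze after PRK". Section 4, item 9 sizes the study on two proportions with an IOP rise, 1.95% and 7.48%, and gives the threshold: "Prior studies have considered intraocular pressure elevation of greater than or equal to 10 mm Hg above baseline clinically significant".

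Item 6 defines the endpoint differently: "The primary outcome measure will be intraocular pressure at each study time point". It allows for raised IOP, in which case "additional IOP lowering drops may be added or the steroid decreased, changed, or increased, based on the clinical picture and physician judgement". It also permits examinations between time points, which are part of "usual care, but will not be considered part of the study data". Scheduled post-operative IOP readings fall at week 1 and months 1, 2, 3, 6 and 12. For these, "Intraocular pressure will be measured by a technician or physician who is masked to the treatment regimen of the patient at each visit".

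For the analysis, item 9 states: "Statistics will be compiled for each variable at the study time points listed in the data collection protocol". Its variables are IOP, haze grade, refraction and the two acuity measures. Adverse events and IOP-lowering treatment are not among them.

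The adverse event text in item 6 covers any untoward sign from surgery to the last visit, whatever its cause, to be logged and described in the chart. Section 6, item 1 names elevated IOP as a steroid complication.

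**The concern.** Three rules act together. IOP may be treated as soon as it is found to be high, extra examinations may be where it is found, and only scheduled readings enter the IOP analysis. Treatment lowers the value that the next scheduled visit measures. A rise that was clinically important enough to treat can thus be missing from the comparison of IOP between arms, although how often rises occur is the question the study asks and is sized for.

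This bears on the conclusion because of how a null result would be read: "If no difference in efficacy or safety is detected between these two regimens, this study will support the use of either steroid regimen". Rises treated between visits would not count toward that reading on safety. Few events are expected, so a small number misclassified in one arm could alter the comparison.

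**Working it through.** **Step 1: follow one eye through the rules.** Suppose IOP is at least 10 mm Hg above baseline at an unscheduled examination, treatment follows, and IOP is below that threshold at all six scheduled post-operative visits.

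- Scheduled-visit IOP (item 6, item 9): no rise.
- Unscheduled reading (item 6): outside the study data.
- Adverse event log (item 6): probably recorded, but without a stated mm Hg threshold.
- Listed statistics (item 9): no adverse event or treatment analysis.

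A rise that is also present at any scheduled visit is still counted.

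**Step 2: how much time lies outside the visit windows.** With 30-day months, the windows are about days 4–10, 20–40, 50–70, 76–104, 150–210 and 330–390. The days between them number 9 (11–19), 9 (41–49), 5 (71–75), 45 (105–149) and 119 (211–329). Coverage is close through month 3 and sparse afterwards. Intervals between actual visits can be longer than the gaps between windows.

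**Step 3: reproduce the plan's sample size.** Inputs from item 9: p1 = 0.0195, p2 = 0.0748, alpha 0.05 (taken as two-sided), power 80%. The mean rate is p̄ = 0.04715.

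n per arm = [1.96·√(2p̄(1−p̄)) + 0.8416·√(p1(1−p1)+p2(1−p2))]² / (p2−p1)²

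= [1.96 × 0.29976 + 0.8416 × 0.29719]² / 0.0553² = 229.4, rounded up to 230 per arm, 460 in all. This matches the plan's 460 eyes when each eye is treated as independent. Expected rises are 230 × 0.0195 = 4.5 and 230 × 0.0748 = 17.2.

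**Step 4: illustrate the effect of missed rises.** With n = 230 per arm,

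power = Φ{[(p2−p1) − 1.96·√(2p̄(1−p̄)/n)] / √([p1(1−p1)+p2(1−p2)]/n)}.

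Base case: (0.0553 − 1.96 × 0.019765) / 0.019596 = 0.845, so power is 80.1%. If a share f of rises is missed, the affected rate is multiplied by (1 − f). For example, with f = 10% in the comparator arm only, p2 = 0.06732 and power is Φ(0.560) = 71.2%.

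| Share missed (assumed) | Both arms | Comparator only | Loteprednol only |
|---|---|---|---|
| 2% | 79.3% | 78.5% | 80.8% |
| 5% | 77.9% | 76.0% | 81.8% |
| 10% | 75.6% | 71.2% | 83.5% |
| 20% | 70.3% | 60.2% | 86.6% |
| 30% | 64.3% | 47.3% | 89.3% |

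In eyes, one, two or three expected rises missed in the comparator arm only (p2 reduced by 1/230, 2/230 or 3/230) give 75.2%, 69.6% and 63.2%. In the last column the higher figure reflects a difference enlarged by undercounting, which is bias and not a gain.

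Every share and count missed is an assumption. The documents give no rate of rises seen only at extra examinations and do not say how the cited study detected its rises. Item 9 also names no test; the two-proportion form is used because it reproduces the stated size.

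**The case against.** The restriction to scheduled visits is defensible. The statement that the IOP measurer is masked is tied to the study visits, and those visits are the same in both arms. Extra examinations depend on the surgeon's judgement, and no masking of the treating physician is stated. Admitting their readings could introduce unequal ascertainment. This stands, and it is why the scheduled-visit analysis should remain primary.

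A reader might infer that scheduled-visit data cannot answer the aim. The documents do not support that. The Objectives do not define incidence as a rise at any moment, so incidence of a rise at any scheduled visit is a legitimate reading and can be computed from the planned data. The plan simply does not state it.

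A reader might also infer that these rises are lost from the trial. That too goes beyond the text. A rise high enough to be treated fits the adverse event definition and should be in the log and the chart. What remains is that the log has no numerical threshold and no listed analysis.

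Finally, the pathway is narrow through month 3, and nothing in the documents suggests that it is common. Equal losses of up to 10% cost less than 5 points of power. The lowest figures need about 3 to 5 of some 17 comparator rises to be missed and none in the other arm. All figures treat eyes as independent; with 115 patients per arm as the unit, nominal power is about 51% before any loss. That is a separate matter, but it means the table is not a statement of the study's actual power.

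**Conclusion.** The point holds in a limited form, and it should be fixed. By its stated rules the plan counts a rise as no rise in the IOP analysis if it is found and treated between visits and is below threshold at every scheduled visit, although the aim and the sample size concern the incidence of such rises. The log probably holds most of them, but no listed analysis uses it.

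The size cannot be determined from the documents. Nor can the direction: loss mainly in the comparator arm would hide a difference, and loss mainly in the loteprednol arm would enlarge one. A reader might conclude that the plan favours loteprednol or that power falls to some particular value. Neither follows, since the power figures rest on assumed shares and independent eyes. Confidence is medium: the rules are clear, but their practical effect is not.

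**What to change.** Keep masked scheduled-visit IOP as the primary outcome and change the following:

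- **Readings after intervention.** State that readings after an IOP-related intervention are kept as measured. Item 6 ends an eye's data collection only for enhancement surgery, so this is presumably intended.
- **Main incidence comparison.** Define it as the incidence of a rise of at least 10 mm Hg above baseline at any scheduled post-operative visit. This is the natural counterpart to the sample size.
- **Exclusion rule, for IOP only.** Replace it with abstraction, from the chart and the adverse event log, of IOP at unscheduled examinations and of IOP-lowering treatment started, with date and reason.
- **Supportive analysis, prespecified.** Compare by arm the incidence of a rise of at least 10 mm Hg at any post-operative examination, scheduled or not.
- **Descriptive tables by arm.** Show IOP-lowering treatment started, steroid changes made because of IOP, IOP-related adverse events, and the number of unscheduled examinations. These are not tested, because the decisions behind them may be unmasked. In addition, only Group 2 has a planned change of drug.

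The cost is some chart abstraction and one added analysis, with no extra visits and no change to patient care. The downside is that unscheduled examinations may be unmasked or more frequent in one arm; that is why the analysis over all examinations is supportive only and why those examinations are counted. It cannot recover a rise that no examination detected.

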For this protocol, an AE is any "on study" untoward medical occurrence (e.g., sign, symptom, disease, syndrome, intercurrent illness) that is experienced by a study subject, regardless of the suspected cause. Both serious and non-serious AEs will be graded on a three-point scale (mild, moderate, severe), and the investigators will assess whether there is a reasonable possibility that study procedure caused or contributed to the AE.

Adverse events that start on Day 0 (Surgery) through the last study visit will be recorded on the study AE log and described in detail in the patient chart. Subjects discontinued early from the study due to an adverse event will be asked to return for a final evaluation. All study-related adverse events will be followed until resolution (or determined to be irreversible, chronic, or stable).

Adverse events that are determined to be unexpected, possibly related to the study procedure, and place subjects at increased risk, will be reported to the Institutional Review Board (IRB) according to their guidelines.

Standard of Care / Research Costs:

All procedures are considered within the standard of care for PRK surgery and will be billed to patients in the usual manner; however, participants will be eligible for a reduced study fee for their surgery and post-operative care. PRK surgery is considered cosmetic surgery and is never billed to insurance. The refractive surgery charge includes standard post-operative examinations up to one year.

Loteprednol 0.5% gel is not available in a generic formulation and is therefore significantly more expensive than generic prednisolone acetate 1% suspension and fluorometholone 0.1% suspension. A request for a donation of loteprednol 0.5% gel for this study has been submitted to Bausch and Lomb and is currently under review. If approved, this drug donation will allow us to eliminate the additional expense of a branded drug for patients that are randomized to the loteprednol group.

If enhancement surgery is deemed necessary during the one-year post-operative period, this will be included based on the patient's initial fee, as is standard of care. Any other costs related to management of adverse events, or if additional refractive correction is necessary at some time after the one-year postoperative period, will remain the patient's responsibility and are not included in the study surgery fee.

7. Are all procedures for research purposes only (non-standard or non-standard of care procedures)?

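### Eyes leave the analysis at enhancement and enhancement is not an outcome, so later refraction and acuity comparisons, and possibly haze, may be biased in an uncertain direction

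*Combined protocol and SAP*

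**What the plan says.** Section 4, item 6 (procedures) sets the rule for each eye. "If enhancement surgery is deemed necessary and performed during the one-year post-operative period", then "study data collection will end for that eye at the time of the enhancement". Earlier data from that eye are kept, and if only one eye is enhanced the fellow eye stays in follow-up to the last planned visit. Item 9 (statistical methods) repeats that "only data collected prior to the enhancement surgery will be included in the statistical analysis" and has statistics compiled for each variable at each study time point.

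On outcomes, item 6 says: "The primary outcome measure will be intraocular pressure at each study time point". It adds: "Secondary outcomes will be grade of corneal haze, manifest refraction, best corrected visual acuity, and uncorrected visual acuity". Enhancement appears in neither list. Item 9 gives no method for values missing after enhancement, no sensitivity analysis and no comparison of enhancement between arms.

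No criterion, expected timing or expected rate for enhancement is given. The closest indication is the costs part of item 6. It covers enhancement within the year under the initial fee and then speaks of further refractive correction that may be needed after the year.

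The Objectives state how a null result will be read: "If no difference in efficacy or safety is detected between these two regimens, this study will support the use of either steroid regimen". Section 6, item 2 says the same.

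**The concern.** Enhancement happens after randomisation and may depend on how the eye has done. If it is refractive re-treatment, as the costs paragraph suggests, the eyes that leave are likely to be those with a poor refraction or poor uncorrected acuity. Those are two of the four secondary outcomes. The eyes still present at a later visit are then a selected group, and the selection may differ by arm.

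If the weaker regimen produces more eyes that need re-treatment, its later summaries improve because those eyes have gone, and the enhancements are not compared anywhere as a result. A real difference could shrink or be missed. That matters here because the plan takes an undetected difference as support for either regimen, so a bias toward similarity would feed directly into the conclusion.

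**Working it through.** **1. What the rule does to a visit summary.** Item 6 stops collection for the eye, and item 9 summarises by time point. An eye enhanced between two visits contributes to the visits before and to none after. Refraction, best corrected acuity and haze are measured after surgery at months 1, 2, 3, 6 and 12, and uncorrected acuity from day 1. The loss can start at any visit after the enhancement, not only at months 6 and 12.

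**2. How far removal is tied to each outcome.**
- Refraction and uncorrected acuity: plausibly tied, given the link to refractive correction in the costs paragraph.
- Haze: possible only. For significant haze, item 6 names added drops or a change of steroid, not enhancement.
- Intraocular pressure: no link is stated.

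**3. The primary outcome: precision only.** Item 9 gives 1.95% versus 7.48%, alpha 0.05, 80% power and 460 eyes. With the pooled normal approximation, two-sided and without continuity correction,

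n per arm = [z₀.₉₇₅·√(2p̄(1−p̄)) + z₀.₈₀·√(p₁(1−p₁)+p₂(1−p₂))]² / (p₂−p₁)², where p̄ = 0.04715,

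= (1.960×0.2998 + 0.8416×0.2972)² / 0.0553² = 229.4, rounded up to 230 per arm or 460 in total. The plan's eye count reproduces, with eyes taken as independent. Power at 230 eyes per arm is 80.1%. If enhancement is unrelated to pressure, losing 5% or 10% of eyes lowers it to 78.0% or 75.8%.

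**4. The later secondary outcomes: an illustration.** The documents give no rates, so everything here is assumed. Let t be the true share of eyes with a poor outcome at a late visit, e the share of poor eyes enhanced before it, and g the share of other eyes enhanced before it. Then

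observed rate = t(1−e) / [t(1−e) + (1−t)(1−g)].

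Take t = 3% versus 10%, a true gap of 7.0 points, with e and g equal in both arms:

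| e | g | Observed rates | Gap (points) |
|---|---|---|---|
| 70% | 0 | 0.9% vs 3.2% | 2.3 |
| 50% | 0 | 1.5% vs 5.3% | 3.7 |
| 30% | 0 | 2.1% vs 7.2% | 5.1 |
| 10% | 0 | 2.7% vs 9.1% | 6.4 |
| 5% | 0 | 2.9% vs 9.5% | 6.7 |
| 5% | 5% | 3.0% vs 10.0% | 7.0 |
| 5% | 10% | 3.2% vs 10.5% | 7.3 |

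First row, worse arm: 0.10×0.30/(0.03+0.90) = 3.2%. Other arm: 0.03×0.30/(0.009+0.97) = 0.9%. Last row, worse arm: 0.095/(0.095+0.81) = 10.5%. Other arm: 0.0285/(0.0285+0.873) = 3.2%.

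**5. When enhancement shares differ by arm.** Take t = 5% versus 10% (true gap 5.0) and g = 3%. If poor eyes are enhanced 30% in the better arm and 60% in the worse, the rates are 3.7% versus 4.4%, a gap of 0.7. With those shares reversed they are 2.1% versus 7.4%, a gap of 5.3. The direction depends on who is enhanced in each arm.

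**6. Power, for orientation.** For 3% versus 10% with 115 independent units per arm, power is 58%. It falls to 45%, 35% or 23% in the 30%, 50% and 70% rows with g = 0. With 230 independent eyes per arm the starting power would be 86%. The right figure lies between, depending on the correlation between a patient's two eyes, so these powers should not carry the argument.

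**The case against.** The strongest reply is that stopping at enhancement is sound. A second operation changes refraction, acuity and possibly haze, so pooling later data would mix its effect with that of the steroid. All earlier measurements stay in, and the fellow eye continues. This stands as a defence of the stop. It does not explain why the event goes uncompared, since enhancement can be compared between arms without any post-enhancement measurement.

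A second reply is that enhancement may reflect the ablation and the nomogram rather than the steroid. If it is unrelated to the outcome, the gap does not move. This also stands: it is the 7.0-point row in the table, and it is why the bias is possible rather than shown.

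Three stronger readings are tempting, and the documents support none of them:
- **That the eyes which healed worst are the ones removed.** The text says only that enhancement is deemed necessary. It gives no criterion and does not link enhancement to healing.
- **That an unmasked surgeon makes the decision.** Item 6 masks the person measuring pressure and the haze grader. It does not say who decides on enhancement or whether that person knows the regimen. Knowledge of treatment could enter, but that is not stated.
- **That the arms must look more alike than they are.** This needs poor eyes to be enhanced preferentially and not at a sufficiently higher rate in the better arm. Other patterns leave the gap unchanged or widen it.

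**Conclusion.** The concern holds as a risk of bias in the later refraction and acuity comparisons, and possibly in haze. The rule and the absence of enhancement from the outcomes are certain. The link to refraction and uncorrected acuity is plausible, and the link to haze is weaker. A pull toward no difference is the more natural expectation, but it is not established.

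The size cannot be fixed from the documents. A true 7.0-point gap is seen as anything from 2.3 to 7.3 points in the equal-share patterns worked above. These are assumed patterns and not bounds, and the poor outcome they refer to is not an endpoint the plan defines. The primary outcome is not shown to be affected beyond a modest loss of precision. The point deserves correction because the plan draws a positive conclusion from a null result and the repair is cheap.

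**What to change.** Keep the stop of data collection at enhancement and keep the planned analysis of pre-enhancement data. Add two things to item 9, with a matching entry in the outcome list in item 6:

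1. Enhancement within 12 months as a secondary outcome compared between arms, with number, reason and timing recorded for each eye.
2. A sensitivity analysis of the later refraction and acuity results in which an enhanced eye counts as a failure against a threshold defined before the data are seen. Do the same for haze where haze was the recorded reason. Report it beside the planned analysis.

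The failure analysis should not replace the planned one. The plan defines no acuity or refraction target at present, and carrying an eye's worst early haze grade forward to month 12 would assume no later change.

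The cost is one extra table, a recorded reason for each enhancement and agreement on the threshold. It needs no added visits and no change to patient care.
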